### Retesting and Confirmatory Testing

One retest is allowed for participants with an “indeterminate” QuantiFERON-TB Gold assay or “borderline” T-SPOT assay, as stated in Section 5.4.1. Patients with 2 indeterminate QuantiFERON-TB Gold assays or 2 borderline T-SPOT assays will require a TST test and CXR; if both are negative, the participant may enroll.

Confirmatory testing with an IGRA is allowed for selected participants who have a positive QuantiFERON-TB Gold assay, positive T SPOT.TB assay, or positive TST who meet all of the following criteria, and are assessed by the investigator as likely having a false-positive test result:

- no risk factors for LTBI,
- no risk factors for increased likelihood of progressing from LTBI to active TB, and
- have never resided in a high-burden country, as detailed in Appendix 10.4.

If the confirmatory test is positive, the participants will be excluded from the study unless he or she completes at least 4 weeks of appropriate therapy for LTBI, based on national or international guidelines (as defined above) and has no evidence of hepatotoxicity (ALT and AST levels must remain  $\leq 2 \times$  ULN) upon retesting of serum ALT and AST levels after at least 4 weeks of LTBI treatment. Such participants must continue and complete appropriate full course of LTBI therapy during the course of the study to remain eligible to participate. If the confirmatory test is negative, these results will be discussed with the medical monitor in order to determine eligibility for the study.

Participants with a negative TST or IGRA can be retested with an IGRA where, in the judgement of the investigator, the initial test result may be a false negative, for example, due to a technical difficulty in administering the TST or due to concomitant immunosuppressant therapy.

### Monitoring for TB During the Study

For all participants, monitoring for TB is to be continuous throughout the study. Every 3 months, the participants will be assessed for risk factors for TB (Appendix 10.4). If the participant has a risk factor, the investigator should conduct a thorough exam to evaluate for TB, including examination of peripheral lymph nodes and documentation of body temperature.

If the participant has a risk factor(s), the investigator should conduct a thorough exam to evaluate for TB, including examination of peripheral lymph nodes and documentation of body temperature. If there are relevant physical findings, an IGRA and CXR or CT should be performed.

### Diagnosis of LTBI During the Study

Participants diagnosed with LTBI during the study must be temporarily discontinued from study drug (Section 7.1.2). If treatment for LTBI is considered to be appropriate, the participant must complete at least 4 weeks of appropriate therapy for LTBI, based on national or international guidelines (as defined above), and have no evidence of hepatotoxicity (ALT and AST levels must remain  $\leq 2 \times$  ULN) upon retesting of serum ALT and AST levels after at least 4 weeks of LTBI treatment. Such participants may then resume study drug and must continue with and complete a full course of treatment for LTBI in order to continue on the study drug.

Noncompliance with LTBI treatment during the study is a reason for permanent discontinuation from study drug (Section 7.1.1).

#### Household Contact

Throughout the study, participants who have had household contact with a person with active TB must be evaluated for TB infection.

#### Prior Treatment for LTBI

Participants who have a documented history of completing an appropriate TB prophylaxis regimen with no history of risk of re-exposure since their treatments were completed and no evidence of active TB are eligible to participate in the study. These participants should not undergo TST or IGRA testing unless advised to do so based on local guidelines.

#### Active TB

Participants with a past history of active TB, without documented treatment by WHO and/or CDC criteria are excluded from the study (Section 5.2).

Participants diagnosed with active TB at screening will be excluded (Section 5.2) and should be referred by the investigator for appropriate TB treatment and follow-up.

If a participant is diagnosed with active TB during the study, the study drug will be permanently discontinued (Section 7.1.1), and the patient will undergo an ETV and then enter the post-treatment follow-up period. The participant should also be referred by the investigator for appropriate TB treatment and follow-up.

### **8.2.8. Clinical Laboratory Tests**

#### Visits and Times

The clinical laboratory tests listed in Appendix 10.2 will be conducted at the study visits specified in the SoA (Section 1.3).

Retesting is allowed during the screening period (see Section 5.4.1).

Additional clinical laboratory tests, including local tests, may be performed at any time during the study as determined necessary by the investigator for immediate participant management or safety or as required by local regulations.

Except where otherwise stated (for example, for postdosing PK sample), samples for laboratory tests should be collected prior to dosing.

#### Central and Local Testing

Unless noted as locally performed (for example, urine pregnancy tests), clinical laboratory tests will be sent to a central laboratory for testing.

#### Provision of Laboratory Test Results

With the exception of laboratory test results that may unblind the study (Section 8.1.2.4), Lilly or its designee will provide the investigator with the results of laboratory tests analyzed by a central vendor.

### Investigator Responsibilities

Investigators or their designees are expected to review laboratory reports in a timely manner throughout the study.

Investigators must document their review of each laboratory safety report.

Any clinically significant findings from laboratory tests that result in a diagnosis and that occur after the participant receives the first dose of study drug should be reported to Lilly or its designee as an AE via eCRF.

#### **8.2.8.1. Pregnancy Testing**

Pregnancy testing is to be performed on all female patients. Participants who are pregnant will be discontinued from the study (Section 7.1.1).

##### Visits and Times

Serum pregnancy test will be done at screening only, and results will be confirmed by the central laboratory.

Urine pregnancy testing will be performed locally at designated scheduled visits through Week 52. The urine pregnancy test must be “negative” prior to administration of study drug at each study visit.

Urine pregnancy testing may be performed at additional time points during the treatment period and/or follow-up period, at the discretion of the investigator or if this is required by local regulations.

If a urine pregnancy test is not available, a serum pregnancy test is an acceptable alternative.

#### **8.2.8.2. Immunogenicity Assessment**

##### Visits and Times

At the visits and times specified in the SoA (Section 1.3), venous blood samples will be collected to determine antibody production against mirikizumab:

- CCI
- CCI

To aid interpretation of these results, CCI

CCI

##### Sample Collection, Handling, and Use

Instructions for the collection and handling of blood samples will be provided by the sponsor.

Immunogenicity will be assessed by a validated assay designed to detect ADAs in the presence of mirikizumab at a laboratory approved by the sponsor. CCI

### Sample Retention

Samples will be retained for a maximum of **CCI** after the last participant visit, or for a shorter period if local regulations and ERBs allow, at a facility selected by the sponsor. The duration allows the sponsor to respond to future regulatory requests related to mirikizumab. Any samples remaining after **CCI** will be destroyed.

### **8.2.9. Hepatitis B Testing**

#### HBV Screening and Interpretation

Participants with acute or chronic hepatitis B infection are excluded from the study (see Section 5.2).

Screening for HBV in this study is performed as follows: an initial test for hepatitis B surface antigen (HBsAg) and anti-hepatitis B core antibody (anti-HBc), followed by a test for HBV DNA in patients who are HBsAg-, anti-HBc+.

#### Exclusion Based on HBV Serology and HBV DNA Testing

Participants with the following screening test results will be excluded from the study (Section 5.2):

- HBsAg+, irrespective of anti-HBc result, *or*
- HBsAg-, anti-HBc+ with detectable HBV DNA.

#### Participants Potentially Allowed into the Study, Based on HBV Serology and HBV DNA Testing

Participants with the following screening test results may be eligible for inclusion, provided they meet the other study entry criteria:

- HBsAg-, anti-HBc-.
- HBsAg-, anti-HBc+ with no HBV DNA detected.

#### Management of Participants with the Following HBV Serology at Baseline: HBsAg-, anti-HBc+, HBV DNA Not Detected

Randomized participants with the following serological pattern at screening will undergo HBV DNA monitoring as described in the SoA (Section 1.3):

- HBsAg-, anti-HBc+, with no HBV DNA detected.

In addition, if such participants experience an elevated ALT or AST level  $>3 \times$  AA ULN during the study, they must have an HBV DNA test and be managed appropriately based on the results of that test.

#### Management of Participants with Detectable HBV DNA During the Study

If HBV DNA is detected during the study, the study drug will be discontinued, and the participant will have an ETV; the participant will then enter the post-treatment follow-up period (Section 7.1). Prior to discontinuing IP, the sponsor recommends that a hepatologist (or a physician with expertise in viral hepatitis) is consulted and that it is determined whether it is appropriate to start antiviral therapy prior to discontinuation of IP or any immunosuppressant or immunomodulatory therapy. However, study drug should not be administered until this consolidation has been completed and after discussion with medical monitor.

If HBV DNA is detected during the study, the investigator should consider using 1 of the following terms to report the AE:

- “Detectable HBV DNA”, if HBV DNA is detected without an increase in aminotransferase levels.
- “Reactivation of hepatitis B”, if HBV DNA is detected, in concert with an increase in aminotransferase levels and/or symptoms and signs of liver disease.

### **8.2.10. Hepatitis C Testing**

Participants with current hepatitis C infection are excluded from the study (see Section 5.2).

Screening for HCV in this study is performed as follows: an initial test for HCV antibody, followed by a test for HCV RNA if the HCV antibody test is positive. Participants with a positive HCV antibody test and detectable HCV RNA will be excluded from the study (Section 5.2).

Participants who test negative for HCV antibody will not be tested for HCV RNA and may be eligible for inclusion in the study.

Participants who have spontaneously cleared hepatitis C infection, defined as:

- a positive HCV antibody test and
- a negative HCV RNA test, with no history of anti-HCV treatment,

[figure not shown]
may be eligible for inclusion in the study, provided they have no detectable HCV RNA on screening for this study.

Any participant with a history of hepatitis C infection who develops elevated ALT >3 times AA ULN within the study will be tested for HCV RNA.

[figure not shown]
Participants with a previous diagnosis of hepatitis C who have been treated with antiviral therapy and achieved a sustained virologic response (SVR) may be eligible for inclusion in the study, provided they have no detectable HCV RNA at screening. Sustained virologic response is defined as an undetectable HCV RNA level 24 weeks after completion of a full, documented course of an approved, potentially curative antiviral therapy for HCV.

If a participant is diagnosed with hepatitis C during the study (detectable HCV RNA), the study drug will be discontinued, and the participant will have an ETV; the participant will then enter the post-treatment follow-up period (Section 7.1). Such participants should also receive appropriate follow-up medical care.

CCI

CCI

### 8.3. Adverse Events and Serious Adverse Events

Investigators are responsible for monitoring the safety of participants who have entered this study and for alerting Lilly or its designee to any event that seems unusual, even if this event may be considered an unanticipated benefit to the participant.

The investigator is responsible for the appropriate medical care of participants during the study.

The investigator remains responsible for following, through an appropriate health care option, AEs that are serious or otherwise medically important, considered related to the investigational product or the study, or that caused the participant to discontinue the investigational product before completing the study. The participant should be followed until the event resolves, stabilizes with appropriate diagnostic evaluation, or is otherwise reasonably explained. The frequency of follow-up evaluations of the AE is left to the discretion of the investigator.

Lack of drug effect is not an AE in clinical studies, because the purpose of the clinical study is to establish treatment effect.

After the ICF is signed, study site personnel will record via eCRF the occurrence and nature of each participant's preexisting conditions, including clinically significant signs and symptoms of the disease under treatment in the study.

In addition, site personnel will record any change in the condition(s), including exacerbation of CD, and any new conditions as AEs.

Investigators should record their assessment of the potential relatedness of each AE to protocol procedure or investigational product, via eCRF.

The investigator will interpret and document whether or not an AE has a reasonable possibility of being related to study treatment, study device, or a study procedure, taking into account the disease, concomitant treatment or pathologies.

A "reasonable possibility" means that there is a cause and effect relationship between the investigational product, study device and/or study procedure and the AE. The investigator answers yes/no when making this assessment.

Planned surgeries and nonsurgical interventions should not be reported as AEs unless the underlying medical condition has worsened during the course of the study.

If a participant's investigational product is discontinued as a result of an AE, study site personnel must report this to Lilly or its designee via eCRF, clarifying, if possible, the circumstances leading to any dosage modifications or discontinuations of treatment.

Care will be taken not to introduce bias when detecting AEs or SAEs. Open-ended and nonleading verbal questioning of the participant is the preferred method to inquire about AE occurrences (see Section 8.3.2.1).

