#### 8.3.1. Serious Adverse Events

An SAE is any AE from this study that results in one of the following outcomes:

- death
- initial or prolonged inpatient hospitalization

- a life-threatening experience (that is, immediate risk of dying)
- persistent or significant disability/incapacity
- congenital anomaly/birth defect
- important medical events that may not be immediately life-threatening or result in death or hospitalization but may jeopardize the participant or may require intervention to prevent 1 of the other outcomes listed in the definition above. Examples of such medical events include allergic bronchospasm requiring intensive treatment in an emergency room or at home, blood dyscrasias or convulsions that do not result in inpatient hospitalization, or the development of drug dependency or drug abuse.

All AEs occurring after signing the ICF are recorded in the eCRF and assessed for serious criteria. The SAE reporting to the sponsor begins after the participant has signed the ICF and has received investigational product. However, if an SAE occurs after signing the ICF, but prior to receiving investigational product, the SAE should be reported to the sponsor as per SAE reporting requirements and timelines (see Section 8.3.2) if it is considered reasonably possibly related to study procedure.

Study site personnel must alert Lilly or its designee of any SAE within 24 hours of investigator awareness of the event via a sponsor-approved method. If alerts are issued via telephone, they are to be immediately followed with official notification on study-specific SAE forms. This 24-hour notification requirement refers to the initial SAE information and all follow-up SAE information. Participants with a serious hepatic AE should have additional data collected using the hepatic eCRF packet (see Section 8.2.11).

Pregnancy (during maternal or paternal exposure to investigational product) does not meet the definition of an AE. However, to fulfill regulatory requirements, any pregnancy should be reported following the SAE process to collect data on the outcome for both mother and fetus.

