### **8.3.1.1. Suspected Unexpected Serious Adverse Reactions**

Suspected unexpected serious adverse reactions (SUSARs) are serious events that are not listed in the IB and that the investigator identifies as related to investigational product or procedure. United States 21 Code of Federal Regulations (CFR) 312.32 and European Union Clinical Trial Directive 2001/20/EC and the associated detailed guidance or national regulatory requirements in participating countries require the reporting of SUSARs. Lilly has procedures that will be followed for the identification, recording, and expedited reporting of SUSARs that are consistent with global regulations and the associated detailed guidance.

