### **8.3.2. Time Period and Frequency for Collecting AE and SAE Information**

Adverse events that begin before the first dose of study drug but after signing of the ICF will be recorded on the AE eCRF.

Investigators are not obligated to actively seek AEs or SAEs in participants once the participant has discontinued and/or completed the study (the participant disposition eCRF has been completed). However, if the investigator learns of any SAE, including a death, at any time after a participant has been discharged from the study, and the investigator considers the event

reasonably possibly related to the study treatment or study participation, the investigator must promptly notify Lilly.

CCI [REDACTED]  
[REDACTED]  
[REDACTED]  
[REDACTED]

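### Protocol Section 8.3 defines a reasonable possibility of relatedness as actual causation, which contradicts the question it explains and leaves no answer for a suspected event

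*Protocol*

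**What the plan says.** Protocol Section 8.3 deals with causality in consecutive statements.

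- What is recorded: "Investigators should record their assessment of the potential relatedness of each AE".
- What is judged: the investigator documents "whether or not an AE has a reasonable possibility of being related to study treatment, study device, or a study procedure".
- What the key phrase means: a reasonable possibility "means that there is a cause and effect relationship between the investigational product, study device and/or study procedure and the AE".
- How it is answered: "The investigator answers yes/no when making this assessment".

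Four rules then use a relatedness judgement.

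- Follow-up (Section 8.3) covers "AEs that are serious or otherwise medically important, considered related to the investigational product or the study, or that caused the participant to discontinue" the product early.
- An SAE between consent and first dose goes to the sponsor under the SAE process "if it is considered reasonably possibly related to study procedure" (Section 8.3.1).
- A SUSAR is a serious event absent from the Investigator's Brochure "that the investigator identifies as related to investigational product or procedure" (Section 8.3.1.1).
- After discharge, the investigator need not look for SAEs, but must promptly notify the sponsor of one that comes to light if it is considered "reasonably possibly related to the study treatment or study participation" (Section 8.3.2).

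**The concern.** The first two statements set a possibility threshold. The definition has no qualifier such as may, suspected or suggests, so taken at its word it asks whether causation exists. Because the answer is binary, an investigator who suspects the drug but cannot establish the link has no category to use and, on the literal text, answers no.

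The answer is more than a recorded data item, because reporting duties depend on it. The population is adolescents on open-label treatment and the group is very small, so each causality judgement carries weight. A threshold that differs between sites, or is set too high everywhere, could keep a suspected late event from the sponsor or send the wrong site judgement into expedited reporting.

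**Working it through.** No arithmetic applies: the plan gives no figure on this point and no planned analysis uses the answer. The check is to take a suspected but unproven event, answer no under the literal definition, and trace each rule.

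1. **Is the contradiction in the current text?** Yes. The sentence is complete, is not affected by redaction, and stands in the body of Section 8.3 rather than in the amendment history. It follows directly after the sentence whose key phrase it defines.

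2. **SAE learned of after discharge (8.3.2).** Notification is conditional on the event being considered reasonably possibly related, which closely tracks the defined phrase. With a no, this rule imposes no duty, and the visible text of the section gives no other route for such an event. This is the clearest loss.

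3. **SUSAR (8.3.1.1).** The definition names the investigator's judgement of relatedness. With a no from the site, the event falls outside the definition as written, although the category is by name one of suspected reactions. The section says related and does not repeat the defined phrase. Linking the two is an inference, though a reasonable one, since Section 8.3 describes no other causality assessment.

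4. **Pre-dose SAE (8.3.1).** With a no, the event is not reported under the SAE process. It is still recorded, because all events after consent are entered in the eCRF. The rule applies only between consent and first dose, and enrolment has stopped (Protocol Section 9.2; SAP Section 3, after 6 participants). It now matters mainly for records already made.

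5. **Follow-up (8.3).** The conditions are alternatives. A serious event, an otherwise medically important event, or one that led to stopping the product is followed whatever the relatedness answer. Follow-up is lost only for an event that meets none of those three conditions.

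6. **SAEs once dosing has started (8.3.1).** Sites must alert the sponsor within 24 hours to any SAE, with no relatedness condition. Unaffected.

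7. **SAP outputs.** The adverse event summaries and listings in SAP Sections 5.6.2 and 5.6.2.1 are not split by relatedness. The registry summaries in SAP Appendix 6 classify events by seriousness and treatment emergence. Unaffected.

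The literal definition therefore removes one sponsor-notification duty outright (post-discharge SAEs), biases one site input (SUSARs), had the same effect on a rule that is now nearly spent (pre-dose SAEs), and trims follow-up at the margin.

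**The case against.** The strongest reply is that the sentence can be read in context. It may name the kind of relationship, cause and effect, whose possibility is being judged. The adjacent sentences, and the wording in 8.3.1 and 8.3.2, all point to the lower threshold, and many investigators will apply it. This stands to the extent that a reader might infer that every suspected event must be answered no, and the documents do not support that certainty. They do support a contradiction that sites could resolve differently, which is itself a defect in a safety definition.

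A second reply is that there are safeguards. SAEs during dosing reach the sponsor regardless of causality. Section 8.3 asks investigators to report anything unusual, and Section 8 asks that safety concerns be discussed with the sponsor at once. The sponsor and a data monitoring committee review safety data. Section 8.3.1.1 commits the sponsor to its own SUSAR procedures. This also stands. A reader might infer that SUSAR reports would be withheld, but those procedures are not in the documents, so only a biased site input can be shown. The safeguards do not remove the gap after discharge, where Section 8.3.2 is the specific rule and makes notification depend on relatedness.

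A third temptation is to infer that suspected events generally drop out of follow-up. The list of alternative conditions in Section 8.3 rules that out.

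**Conclusion.** The definition is wrong as written. It contradicts the possibility standard in the two sentences before it and, with a yes/no answer, leaves no place for a suspected event. The live consequences are the post-discharge SAE duty and the investigator's contribution to SUSAR identification. The pre-dose rule is mostly moot, and the loss of follow-up is confined to events that are non-serious, not otherwise medically important, and did not lead to discontinuation.

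There is no numerical magnitude. With 6 participants a reader might compare one related SAE in six with none in six, but no planned table reports a related-SAE rate, and the SAE would be listed either way. No efficacy result, sample size or planned safety display changes.

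The conclusion assumes that the relatedness wording in Sections 8.3.1.1 and 8.3 (follow-up) refers to the same yes/no assessment, and that neither the redacted text nor the eCRF instructions, which are not available, set a different threshold. How often the literal reading has been applied, and whether any SAE has been affected, cannot be told from the documents.

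**What to change.** In Protocol Section 8.3, replace the definition with a possibility standard, for example: a reasonable possibility means that the facts of the case suggest the investigational product, device or procedure may have caused or contributed to the event; established causation is not required. Use that same term in Sections 8.3, 8.3.1, 8.3.1.1 and 8.3.2, so that each rule plainly refers to one assessment. Inform sites through the usual amendment and ethics route, and have investigators reconfirm the causality answer for any SAEs already recorded, including those in participants who have left the study. The SAP needs no change.

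The cost is a short wording change, the amendment and ethics handling, a site communication, and a recheck of existing SAE records, whose number the documents do not give. The downside is slightly more events marked related and possibly more expedited reports.
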